## 6.7 Participant Withdrawal

Participants will be advised that they are free to withdraw from the study at any time including before, during or after the treatment has ceased. They may notify any of the research team members of their withdrawal. They may withdraw without any consequences or negative impact on their relationship with the University, the University SPEECH Clinic, the researchers, or the profession (Speech Pathology). The participant's individual data will stop being collected at the point of their withdrawal and their withdrawal will be recorded in the data management system (RedCap) within one business day of their withdrawal.

### 6.7.1 Reasons for withdrawal

If the participants withdraw from the study prior to the conclusion, they will be asked for their reasons for withdrawal and if they consent to us retaining data that has already been

collected. If the participants consent to their data being retained, the data will be analysed using Intention to Treat Analysis.

The researchers may also withdraw participants from the study if they are non-compliant with the treatment protocol (e.g., cannot commit to the sessions) or are no longer eligible for the study due to changes in medical status (e.g., onset of stroke). If this occurs then the USYD HREC will be advised.

#### *6.7.2 Handling of withdrawals and losses to follow-up*

Intention to Treat (ITT) will be used to statistically analyse the results if there is loss to follow up or with participant consent, following withdrawal.

#### *6.7.3 Replacements*

Replacements will be sought for participants who withdraw from the study to ensure a minimum data set of  $n=3$

### **6.8 Expected Duration of Study**

The study duration is 24 months. We anticipate recruitment of participants to commence October 2024, pending ethics approval and necessary administrative approvals.

### **6.9 Ethics Approval**

Ethics approval will be sought from The University of Sydney Human Research Ethics Committee (HREC).

### **6.10 Modifications to the Protocol**

Any amendments will be submitted to each HREC for review prior to implementation as per HREC guidelines. Once approved by The University of Sydney, they will be notified to ANZCTR.

### **6.11 Protocol Violations**

#### *6.11.1 Treatment Fidelity*

To ensure treatment fidelity, all participants will be treated as per the protocol. A speech pathologist with at least 5 years of experience in managing swallowing difficulties will provide the intervention. Treatment fidelity will be reviewed by an independent speech pathologist for a random 20% selection of intervention sessions during the study using a checklist to ensure adherence to the intended protocol.

#### *6.11.2 Data Monitoring*

All adverse events will be recorded and reported using the university systems including RiskWare, MyResearch Ethics and the FMH Clinical Governance procedures. USYD clinical trial support office procedures will be followed.

### **6.12 Participation Reimbursement**

All research participants will receive a free speech pathology assessment and access speech pathology intervention as part of their participation with a discharge report following the block of therapy.

### **6.13 Continuation of therapy**

The trial will continue provided that no adverse/serious events occur until either of the following has been met: (i) enough participants have been recruited, or (ii) the study period has ended.

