### **7.2 Potential Risks and Proposed Benefits**

#### *7.2.1 Potential Risks*

It is unlikely that participants will experience any harm when receiving therapy. Ultrasound as a biofeedback in a skill-based training targeting orolingual control has also been safely used in the head and neck cancer and other populations.

This is a relatively low-risk project and does not pose significant foreseeable risks to the participants. It may involve mild distress sometimes as tasks may be difficult for the participant. However, speech pathology care in this study is not different from usual practice.

The participants may experience fatigue and frustration during assessments or treatment. The speech pathologist will note signs of fatigue or frustration and give the person a short break if these occur.

As this is a trial study with adults who have a neurodegenerative disease, there is a risk of no improvement or decline in swallow function at the end of the study due to the progression of the disease. The participants are informed of this at recruitment. Breaches of privacy or confidentiality may pose a risk. This is covered in Section 10 Data Management.

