## **8. SAFETY CONSIDERATIONS**

### **8.1 Adverse event definition, risk assessment and mitigations**

An adverse incident is a harmful, unpleasant, or undesirable response, reaction, or outcome experienced by a research participant or researcher. In the context of this study, Serious Adverse Events include choking or chest infection resulting in hospitalisation or death.

The risk of serious adverse events is no greater than if the participant does not take part in this study. Participants in this study will be medically stable and eating and drinking in the community. Additionally, there is an exclusion criteria excluding participants who have a recent serious upper respiratory tract infection, and the therapy protocol will be carried out by a qualified and experienced speech pathologist with current CPR certification.

The researcher will contact the participants one day prior to each treatment session to ask about their health and discuss postponing the session and referral to their GP if they are unwell. The researcher will also ask the participant about their health again at the beginning of each session to confirm that they are fit to continue. If there are any concerns, they will discuss postponing the session and referral to their GP or other health practitioner with the participant.

Other potential anticipated adverse events include fatigue from the intensity of the therapy protocol and feeling full or nauseous from having to eat or drink as part of the therapy. These risks will be mitigated through:

- scheduling sessions at least 2 hours after a meal and taking their medication as normal
- reminding participants to continue with their current medication regime and that it should not be impacted by this study participation
- informing participants beforehand that they will need to eat and drink during the therapy sessions.
- and regular breaks in the session

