### **8.2 Assessment and Documentation of Adverse Events**

Participants will be advised that they should report any adverse events including fatigue, pain, nausea, vomiting, fever, cough, cold, throat irritation.

In the event of a medical emergency (i.e., a serious adverse event related or unrelated to the study), an ambulance will be called, security staff at SWHB will be notified and SWHB safety procedures followed.

In either case, the adverse event or serious adverse event will be reported in Riskware (and technology relevant to the site), to the HREC and ANZCTR

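### Section 6.13 lets the trial continue only while no adverse event occurs, yet Sections 8.1 and 8.2 anticipate mild adverse events and the protocol manages them while the trial goes on

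*Protocol*

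**What the plan says.** The continuation condition is one sentence in Section 6.13: "The trial will continue provided that no adverse/serious events occur until either of the following has been met". The two end conditions that follow are sufficient recruitment, with no number given, and the end of the study period. Nothing in the section restricts the condition to events that are serious, related to treatment, or repeated.

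Section 8.1 defines the relevant event very broadly: "An adverse incident is a harmful, unpleasant, or undesirable response, reaction, or outcome experienced by a research participant or researcher". It describes the serious class separately ("Serious Adverse Events include choking or chest infection resulting in hospitalisation or death") and then lists milder events that the investigators expect: "Other potential anticipated adverse events include fatigue from the intensity of the therapy protocol and feeling full or nauseous from having to eat or drink". Section 8.2 tells participants that "they should report any adverse events including fatigue, pain, nausea, vomiting, fever, cough, cold, throat irritation". Section 7.2.1 adds: "The participants may experience fatigue and frustration during assessments or treatment".

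The response to these milder events is always local. Section 7.2.1 gives a short break. Section 8.1 spaces sessions away from meals, allows breaks, and discusses postponement and GP referral when a participant is unwell. The Probes text in Section 6.2 allows the sessions to be altered for fatigue. Sections 6.11.2, 8.2 and 8.3 require recording and reporting. None of these places mentions ending the trial.

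**The concern.** The rule on whether the trial goes on and the safety section use the same term for different things. In Section 8 an adverse event is something to expect, mitigate, record and report. In Section 6.13 the occurrence of one removes the condition for continuing.

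If the team follows 6.13 as written, a single report of tiredness after a therapy session closes the trial. If the team treats that as absurd and carries on, it departs from its own protocol, and nothing in the document then says which events bear on continuation or who decides. A rule that protects participants should not have to be guessed at, and a pilot that meets its first case of fatigue should not have to settle the meaning of its continuation rule at that moment.

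**Working it through.** **1. The passages side by side.**

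| Question | Section 6.13 | Sections 7.2.1, 8.1, 8.2 and Probes (6.2) |
|---|---|---|
| Which events count? | Adverse/serious, not qualified | Adverse events defined broadly; serious ones described separately |
| Are mild events expected? | Not addressed | Yes: fatigue, fullness and nausea (8.1); fatigue and frustration (7.2.1) |
| What follows from one? | The condition for continuing fails | Break, altered or postponed session, GP referral, record and report |

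A fatigue report falls in both columns, and the last row gives incompatible consequences.

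**2. Does another section narrow 6.13?** Section 8.2 names adverse events and serious adverse events as two classes, and Section 8.3 gives them different reporting limits (72 hours and 24 hours). The protocol therefore has the vocabulary to restrict 6.13 to serious events and does not use it there. Section 6.7.1 covers withdrawal of individuals, and Section 6.11.2 covers recording and reporting. No section qualifies 6.13.

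**3. How often would the literal condition fail?** The protocol states no event rate or stopping probability, so there is no figure to reproduce. Inputs:

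- Number of participants: n = 6 (Synopsis; Section 6.3).
- Chance p that a participant has at least one listed event during participation: assumed, with a range shown.
- Independence between participants: assumed.

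P(at least one event) = 1 − (1 − p)^n.

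- p = 0.05: 1 − 0.95^6 = 26.5%
- p = 0.10: 1 − 0.90^6 = 46.9%
- p = 0.20: 1 − 0.80^6 = 73.8%
- p = 0.50: 1 − 0.50^6 = 98.4%

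A 95% chance of failure needs p = 1 − 0.05^(1/6), about 0.39.

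**4. The same by session.** The schedule in Section 6.2 takes treatment probes at the first and third session of each week. The Probes text describes the same probes as falling on the first and last session, for four weeks. That implies 3 × 4 = 12 sessions each and 6 × 12 = 72 in all. With an assumed independent risk per session, 1% gives 51.5%, 2% gives 76.7% and 5% gives 97.5%. A 95% chance needs about 4.1% per session.

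**5. What these figures overcount.** The condition in 6.13 applies only until enough participants have been recruited or the study period ends. Recruitment is rolling, so events after the last needed enrolment fall outside the rule, yet the formula counts them. If five participants had finished before the sixth enrolled, only those five would count: 1 − (1 − p)^5 = 22.6%, 67.2% and 96.9% at p = 0.05, 0.20 and 0.50. Overlapping participation would lower this further. For six participants the figures in step 3 are therefore an upper guide. If the feasibility participant in Section 6.3 is counted in addition, n = 7 gives 30.2%, 79.0% and 99.2%, with the same caveat.

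**The case against.** The strongest reply is that this is a drafting slip. Read as a whole, the protocol separates grave events from tolerable ones and answers fatigue with a rest, and nobody would close the trial because a participant felt tired. On that view the slash in 6.13 simply means serious adverse events. This may well be the intention, but the text does not say so, and Sections 8.2 and 8.3 keep the two classes apart. The reply explains how the sentence may have arisen; it does not remove the conflict.

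Three stronger readings are tempting and are not supported.

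- A reader might infer that the trial would almost surely stop early. That depends on an event rate that the protocol does not give. At 5% to 10% per participant the chance is about 26% to 47%, even before allowing for the overcount.
- A reader might infer that, without a workable 6.13, unblinded researchers would decide ad hoc while watching results accumulate. Section 6.14 makes graphing the first analysis step and does not say that graphs are reviewed during accrual. Section 6.4.3 blinds the outcome assessors to phase. Sections 6.11.2, 7.1, 7.5 and 8.3 provide reporting, ethics oversight and clinical governance. Those arrangements are real, although none states which events bear on continuation.
- A reader might see a conflict between six and three participants. Six is the recruitment target allowing for attrition (Synopsis; Section 6.3). Three is the minimum data set that replacements are meant to secure (Section 6.7.3). The two are compatible.

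**Conclusion.** The point holds as an internal contradiction. Section 6.13 is wrong as written: it cannot be followed together with Sections 7.2.1, 8.1 and 8.2 and the Probes text, and setting it aside leaves the protocol with no stated continuation rule. That conclusion rests on the wording alone.

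The size is uncertain. The chance that the literal condition fails among six participants runs from about 26% to about 98% over assumed per-participant risks of 5% to 50%, with independence assumed and with some overcounting of events after recruitment closes. The figures show that failure is a practical possibility across that range; they do not show that it is near certain. No endpoint, effect size or analysis is affected directly. What is at stake is a workable safety condition and adherence to the protocol.

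**What to change.** Reconcile Section 6.13 with Sections 8.1 to 8.3 so that both use the same defined categories of event. State in 6.13 which category triggers a review of whether the trial continues, and which person or body carries out that review. Which events belong in that category, and what should follow from them, is for the investigators and the ethics committee to decide.

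As a minor clarification in the same sentence, tie the recruitment end condition to the planned number of participants.

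The cost is the rewording of one paragraph, submitted to the ethics committee as an amendment under Section 6.10 and then notified to the registry. No change to data collection or analysis follows from it.

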### **6.14 Statistical analyses**

As per standard procedure for single case within participant studies, experimental and control measures will first be graphed and visually inspected for change. If the visual inspection indicates change over time, statistical analysis will be completed. As multiple, repeated measures will be taken for each participant, the data will first be analysed for correlations. If the correlation coefficient was not significant, the assumption of independence in measurements will be made, and effect sizes within participant will be calculated using  $d_2$  as this measure is appropriate for single case data (Beeson & Robey, 2006).

In the presence of serial dependency between data points, the data will be analysed using percent of nonoverlapping data (PND) (Scruggs, Mastropieri & Casto, 1987). PND is a commonly used calculation to measure change in measures taken across research phases. The highest data point in the baseline (A1) phase is compared across all research phases. The number of data points either above or below that value is calculated as a percentage of the total number of data points. The higher the number of nonoverlapping data points, the stronger the effect.

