### 2. SYNOPSIS

TITLE	Effect of Swallowing Therapy on Efficiency of Eating and Drinking in People with Parkinson’s Disease using Principles of Motor Learning and Ultrasound Biofeedback
CLINICAL PHASE	I/II
STUDY TYPE:	Behavioural intervention
PRIMARY HYPOTHESES	Participants will show an improvement in swallowing outcomes with the use of rehabilitation combining principles of motor learning and ultrasound biofeedback. No improvement in control outcomes will be observed.
DESIGN	Part 1 - Single Case Experimental Design to determine feasibility of treatment paradigm in a single participant with PD followed by Part 2 - a multiple baseline within participants Single Case Experimental design to determine treatment efficacy.
BLINDING/MASKING	This is a pilot, behavioural intervention trial. Therefore, treating clinicians and participants cannot be blinded to intervention.

	Clinicians assessing outcome measures will be blinded to the sequence in which the probe data is collected and the stage of the study the participant is in.

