#### *6.4.3 Randomisation and Blinding Processes*

As it is a behavioural study, participants and the therapist will not be blinded to the intervention. However, the assessors will be blinded to the sequence in which the probe data is collected (i.e., the assessor will review the task recordings to obtain the probe data and will not know which week a specific recording was obtained). This will be achieved by getting an independent person to re-order the recordings of sessions so that they are not chronological, and the assessors will evaluate the outcome measures without knowing if they are from the baseline or intervention phase. Participants will be randomised into different lengths and onset of baseline phase prior to assessment.

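### The blind covers scoring of the recordings, but no masking is provided for the visual inspection on which all the statistics depend

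*Protocol*

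**What the plan says.** **Blinding.** The synopsis states: "Clinicians assessing outcome measures will be blinded to the sequence in which the probe data is collected". It extends this to the stage of the study. Section 6.4.3 explains what it means in practice: "the assessor will review the task recordings to obtain the probe data and will not know which week a specific recording was obtained". The method is "getting an independent person to re-order the recordings of sessions so that they are not chronological". The same section says that "participants and the therapist will not be blinded to the intervention". Participants, therapist and assessors are the only parties whose blinding is addressed.

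**Analysis.** Section 6.14 opens with the step that "experimental and control measures will first be graphed and visually inspected for change". It continues: "If the visual inspection indicates change over time, statistical analysis will be completed". Only then do the check for serial dependency and the effect sizes follow: d2 if the points are taken as independent, percent of nonoverlapping data (PND) if not. The section does not say who inspects the graphs, how many people do so, whether phase or measure labels are visible, or what counts as change.

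**Hypothesis.** The synopsis predicts improvement in the swallowing outcomes and no improvement in the control outcomes.

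**The concern.** Re-ordering the recordings hides time from the person who scores them. A graph read for change over time has to put the time order back. The protection described in section 6.4.3 therefore ends where the reading of the graphs begins, and nothing takes its place.

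Because the hypothesis predicts opposite readings for the two kinds of series, a reader who recognises the measure has an expectation for every graph. Leniency on swallowing and strictness on controls both push towards the hypothesis. There is no separate comparison group, so the contrast between swallowing and control measures carries much of the weight in attributing change to treatment. A biased reading would affect both the efficacy conclusion and the specificity conclusion, in the same direction.

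**Working it through.** The protocol gives no threshold, error rate or decision rule for the inspection, so there is no figure to reproduce. The check is one of text, followed by an illustration.

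**1. What is masked at each step**

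| Step | Done by | Masking described |
|---|---|---|
| Treatment | Therapist | None (6.4.3) |
| Scoring of recordings | Assessors | Week and phase hidden by re-ordering (2, 6.4.3) |
| Visual inspection | Not stated | None described (6.14) |
| d2 or PND | Not stated | Arithmetic on blind-scored values, run only if inspection shows change (6.14) |

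**2. How many readings.** There are 6 participants (synopsis; 6.3), 2 primary measures and 4 control measures (6.5). Counting one series per measure: 6 × (2 + 4) = 36 readings.

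**3. What follows from a wrong call.** This assumes that the condition in 6.14 is applied series by series, which is the natural reading but is not stated.

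- *An unchanged swallowing series is called changed.* An effect size is computed from blind-scored data and would tend to be small. The error can be seen, although 6.14 sets no value at which the call would be withdrawn.
- *A control series that did change is called flat.* No statistic is triggered. Nothing in 6.14 would reveal the error.

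The second route does more damage, because it removes the evidence that would correct it.

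**4. Illustration under no true effect.** The inputs from the protocol are 6 or 9 probes in each of A1 and A2, 8 in B (2 per week × 4 weeks), 2 primary and 4 control measures. The assumptions are normal data, measures independent of one another, lag-one correlation 0 or 0.3, and 40,000 simulated participants per setting. The reader is represented by a cut-off on

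d = (mean A1 − mean A2) / √[(s²A1 + s²A2)/2], with positive values meaning improvement.

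The hypothesised pattern is d above the swallowing cut-off for at least one primary measure and |d| at or below the control cut-off for all four controls.

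| Cut-offs (swallowing / control) | 6 probes, corr. 0 | 6 probes, corr. 0.3 | 9 probes, corr. 0 | 9 probes, corr. 0.3 |
|---|---|---|---|---|
| 1.0 / 1.0 | 7.0% | 7.7% | 4.1% | 7.4% |
| 0.75 / 1.25 | 16.6% | 17.4% | 11.9% | 18.3% |
| 0.5 / 1.5 | 33.0% | 32.2% | 27.5% | 34.2% |

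Check on the first column: the measures are independent, so the result should be close to the product of the two parts. 0.111 × 0.619 = 0.069; 0.210 × 0.794 = 0.167; 0.365 × 0.900 = 0.329. These agree with 7.0%, 16.6% and 33.0%.

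**5. How far phase can be hidden.** Probes are taken three times weekly in A1 and A2 and twice weekly in B (6.2), so a calendar axis shows the phase through spacing alone. Plotting by session number removes that clue. The count remains: 6 + 8 + 6 = 20 points or 9 + 8 + 9 = 26 points, and a reader who knows the design can infer the schedule from the total. Masking of the measure does not have this weakness, provided units and scale are removed.

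**The case against.** **The protocol is silent, and an analysis plan could hold the detail.** A reader might infer that the inspectors will see the phase and measure labels. The protocol does not say so; it says nothing on the matter. The supportable statement is that no masking is provided for. The point survives because who is blinded belongs in a protocol, this one has a blinding section that stops at the assessors, and 6.14 itself makes the inspection the condition for any statistics.

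**The effect sizes are safe.** A reader might infer that expectation can inflate d2 or PND. It cannot: once run, they are arithmetic on scores taken from re-ordered recordings. This stands, and it limits the concern to how the graphs are read and whether the statistics are run.

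**The blind already protects the subjective part.** This is partly true. The blinded scoring includes a perceptual intelligibility rating and ultrasound ratings of swallowing components, so it would be wrong to say that only objective steps are blinded. Judging whether a graph shows change is still a further judgement, and it is unprotected.

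**This is a small pilot, and visual inspection is customary in single-case work.** Both are fair. The point is not against inspection, and no confirmatory threshold is at stake. The synopsis does, however, give Part 2 the purpose of determining treatment efficacy.

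**Conclusion.** The concern holds in this form: the protocol's masking covers scoring, none is provided for the inspection that decides whether statistics are run, and the hypothesis gives an informed reader opposite expectations for the two kinds of series. A control series called flat then gets no effect size that could expose the error, if the condition is applied series by series.

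The size of the bias cannot be derived from the documents. The illustration shows direction and rough scale only: about 4–8% of participants with no true effect show the hypothesised pattern under a common cut-off, about 12–18% under a modest difference in cut-offs, and about 28–34% under a large one. The cut-offs are assumptions. The figures describe the visual call, not the effect sizes that may follow it. They should not be read as the trial's error rate, nor as evidence that biased reading is likely.

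This does not stop the trial. It should be corrected before any graph is read.

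**What to change.** Amend section 6.14 as follows.

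1. Compute and report the planned effect size for every primary and control series, whatever the inspection shows. This closes the route by which a wrong call on a control series goes unseen, and it does not depend on masking.
2. Have the graphs read by a blinded assessor who is not involved in treatment. Remove measure names, units and phase labels, rescale the values, orient all series the same way and plot by session number. The independent person who already re-orders the recordings shuffles swallowing and control series together.
3. Record whether and where each series changes, lock the calls, then unmask and compare them with the actual onset of treatment.

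Section 6.4.3 should name the graph reader among those blinded.

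The cost is a few hours of graph preparation by people already in the plan and one extra step before unmasking. Phase masking will be imperfect because the number of probes can reveal the schedule, so masking of the measure is the main protection.

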## **4. AIMS & HYPOTHESES**

### **4.1 Aims:**

- 1) To develop and determine the feasibility of a training program which targets movement of food / liquid in the mouth with the use of ultrasound visual feedback and principles of motor learning to rehabilitate oral phase swallowing disorders amongst PwPD.
- 2) To determine the effectiveness of the developed training program on improving the efficiency of swallowing and QOL in PwPD.

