## Probes

As shown on page 8, Probes for Phase A1 and A2: The TWST and TOMASS and a measurement of maximum phonation time and a 30 second monologue will be obtained 6 times for those allocated in the 2-week baseline periods and 9 times for those allocated in the 3-week baseline period.

Probes for Phase B: Treatment probes will be taken twice weekly (on the day of the first and last therapy session each week) for 4 weeks. Treatment probes will be identical to the baseline probes and will be collected immediately before therapy commences on that day.

The probes will take approximately 30-40 minutes and breaks will be provided if a participant experiences fatigue.

After the end of Phase B, a repeat assessment will be completed (identical to the one conducted at the start of the treatment program) by a qualified speech pathologist. Participants will also be asked to complete a Theoretical Framework of Acceptability Questionnaire to understand their acceptance and the feasibility of the intervention.

As this is a pilot, the frequency and duration of the treatment sessions, the duration and frequency of breaks provided, the type of foods and fluids used, the amount and type of feedback provided and the number of times the participant is asked to swallow and sets of swallows may be altered based on participants' fatigue level and response to the therapy protocol.

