### **6.3 Population/ Calculation of sample size**

Sample size calculation: This is a phase 1 study to acquire data for a sample size calculation. Considering no protocol exists for ultrasound visual feedback in dysphagia rehabilitation in people with Parkinson's, the researchers will first aim to assess the feasibility of use with a single participant. Subsequently, n=6 will be recruited to allow for attrition expected in behavioural rehabilitation. This follows a similar sample size to other pilot studies (Blyth, McCabe, Madill, & Ballard, 2017).

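### Section 6.14 calculates effect sizes only where the graph already looks changed, so flat control series get no number and small-to-moderate effects are reported too large

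*Protocol*

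**What the plan says.** Section 6.14 (Statistical analyses) sets an order of work. First, "experimental and control measures will first be graphed and visually inspected for change". Next comes the condition: "If the visual inspection indicates change over time, statistical analysis will be completed". Only after that does the section describe a check for correlation between repeated measurements. If that correlation is not significant, "effect sizes within participant will be calculated using" d2. If there is serial dependency, PND is used instead. Nothing in the protocol provides an effect size for a series judged unchanged.

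Three other places bear on this:

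- The Synopsis includes a prediction about the control measures in its primary hypotheses: "No improvement in control outcomes will be observed".
- Section 4.1 gives the second aim: "To determine the effectiveness of the developed training program on improving the efficiency of swallowing and QOL in PwPD".
- Section 6.3 gives the use to be made of the results: "This is a phase 1 study to acquire data for a sample size calculation".

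**The concern.** The rule decides whether a result is quantified by looking at that same result. Two consequences follow.

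The first concerns the control measures and needs no arithmetic. The four control measures are there to show that any change is specific to swallowing. The expected finding is a flat control series, and under the rule a flat series receives no d2 or PND. A number appears only when the control measure seems to have moved. The specificity argument then rests on a visual judgement on one side and an effect size on the other.

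The second concerns the swallowing measures. If d2 is calculated only when the graph looks changed, the values reported are those in which chance helped to produce a visible difference. Participants who did not respond contribute no value to pull the average down. Where true effects are small to moderate, the reported set lies further from zero than the truth, and it may feed the planning of a later trial.

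**Working it through.** **Inputs from the protocol.** The Probes paragraph says that measures in A1 and A2 are "obtained 6 times for those allocated in the 2-week baseline periods and 9 times for those allocated in the 3-week baseline period". The schedule gives three probes a week: 3 × 2 = 6 and 3 × 3 = 9, so the probe counts reproduce. Section 6.3 gives six participants and section 6.5 lists four control measures, which makes 4 × 6 = 24 control series. The protocol gives no expected effect, no formula for d2 and no criterion for visible change.

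**Assumptions, not in the protocol.** d2 = (A2 mean − A1 mean) / pooled SD, signed so that improvement is positive. Probes are normal and independent. The graph is taken to look changed when |d2| exceeds a threshold g of 0.8 to 1.0. The threshold is two-sided because section 6.14 speaks of change, not improvement, and section 7.2.1 foresees possible decline.

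**Formula.** With n probes per phase and true effect δ, d2 × √(n/2) follows a noncentral t distribution with 2n − 2 degrees of freedom and noncentrality δ√(n/2). For n = 6 this is 10 degrees of freedom and 1.73δ. Without the condition the mean of d2 is 1.084 × δ; the excess over δ is ordinary small-sample bias. With the condition, the mean is E(d2 given |d2| > g). Simulation of 200,000 series per case agrees to within about 0.01.

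**Results, 6+6 probes.**

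| True d | Mean d2, all series | Share passing (g = 0.8; 1.0) | Mean d2 of those passing (g = 0.8; 1.0) |
|---|---|---|---|
| 0 | 0.00 | 20%; 11% | 0.00; 0.00 |
| 0.5 | 0.54 | 34%; 23% | 1.16; 1.34 |
| 1 | 1.08 | 64%; 52% | 1.46; 1.60 |
| 2 | 2.17 | 98%; 95% | 2.20; 2.24 |
| 3 | 3.25 | 100%; 100% | 3.25; 3.25 |

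Relative to the unselected mean, the reported mean is 1.16/0.54 = 2.1 to 1.34/0.54 = 2.5 times as large at d = 0.5. It is 1.46/1.08 = 1.4 to 1.60/1.08 = 1.5 times as large at d = 1, and 2.20/2.17 = 1.01 to 2.24/2.17 = 1.03 times at d = 2.

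With no true effect, the series that pass are individually extreme (mean |d2| about 1.16 to 1.35), but the signs cancel.

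**Sensitivity.**

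- With 9+9 probes, the reported means are 1.11 to 1.29 at d = 0.5 (0.53 unselected) and 1.33 to 1.46 at d = 1 (1.05 unselected).
- Widening the threshold to 0.5 to 1.5 with 6+6 probes gives 0.89 to 1.84 at d = 0.5 and 1.29 to 2.01 at d = 1.

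**Control series.** If no control measure truly changes and all participants have 6+6 probes, about 24 × 0.196 = 4.7 (g = 0.8) or 24 × 0.114 = 2.7 (g = 1.0) of the 24 series would receive an effect size, each because it looked changed. The other 19 to 21 would receive none.

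**The case against.** Section 6.14 presents visual inspection first as standard for single-case studies, and nothing here disputes that. The objection is only to using it to decide whether a calculation is done. Nor is this a detail left to an analysis plan: the protocol states the condition, and a plan that calculated every effect would depart from it.

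Several counter-arguments do stand and limit the point.

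- **The unit is not stated.** Inspection might be judged per series, per participant or overall. If it is per participant, someone whose swallowing visibly changes would have the control measures analysed too.
- **Flat series are not hidden.** Every measure is graphed, and de-identified data are to be archived subject to consent. They are unquantified, not suppressed.
- **The modelled gate is a simplification.** A reader would see the whole graph, including eight phase B probes (2 a week × 4 weeks), whereas the calculation selects on the same A1–A2 difference that it then reports. A simulated gate with random error in the reader's judgement (an arbitrary amount) gave 1.01 at d = 0.5 and 1.48 at d = 1: less inflation at 0.5, similar at 1. No magnitude is given for series that go to PND.

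Three stronger readings are tempting and not supported. A reader might infer that the control hypothesis is never quantified, but a control series that looks changed does get a number. A reader might infer that all reported effects are inflated, or that efficacy would appear on average where none exists. The first fails for large effects, and the second fails under a two-sided condition. A reader might also square the inflation ratio and infer that a later trial would be too small by a known multiple. That does not follow: d2 as assumed here is scaled by one person's probe-to-probe SD, a group trial would be sized on variation between participants, and section 6.3 does not say that d2 or PND will be the planning input.

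**Conclusion.** The point holds in limited form and should be fixed. As written, section 6.14 makes all quantification depend on change already being visible. The consequence for the control measures depends on no assumed effect size, only on reading the condition series by series: absence of improvement can be contradicted numerically but not supported, and there is no common scale for comparing swallowing with control change.

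The bias in the reported effect sizes is real, but its size cannot be fixed from the protocol. Under the stated assumptions it is large at a true d of 0.5, moderate at 1, slight at 2 and absent at 3. These figures illustrate the mechanism and do not forecast this trial's results.

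**What to change.** In section 6.14, delete the sentence that makes statistical analysis conditional on visual inspection. State instead that the prespecified effect measure (d2, or PND where there is serial dependency) will be calculated for every participant on both primary outcomes and all four control measures, whatever the graph shows. Report the visual analysis next to these values, not as a condition for them. The change should be made before the graphs are inspected. Intervals and table layout can be left to the analysis plan.

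The cost is one amended sentence and a few more calculations on data that will be collected anyway. Some reported effects will be smaller.
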